12.1.5 Safety analysis set

The safety analysis set is a subset of randomised analysis set including patients who took at least one investigational product dose.

12.1.6 Last Observation Carried Forward (LOCF)

The last observation carried forward approach will be applied to exploratory continuous endpoints only. This means that for a specific time-point post-baseline, analyses will be based on measurements available at that time-point or the last post-baseline measurement prior to the time-point, if no measurement is available at that time-point.

Furthermore, an observed cases analysis without any imputation of missing values will be conducted if a relevant number of missing values occurs. Details will be specified in the SAP before breaking the blind.

12.2 Methods of statistical analyses

12.2.1 Analyses of the primary and secondary endpoints

The proportion of patients reaching $HbA_{1c} < 7\%$ after 52 weeks of treatment without confirmed or severe hypoglycaemia (for definition of hypoglycaemic events, see Section 11.2.3) will be analysed using the Cochran-Mantel-Haenszel (CMH) method for the odds ratio (OR), including a stratification variable for the age group (<75 versus \geq 75 years).

The primary efficacy analysis will be performed on the safety analysis set using the above mentioned CMH approach providing statistical test results and 95% confidence intervals for the OR comparing treatments. There will be no re-assignment of treatments for this analysis, each patient will be analysed as randomised.

In order to assess the influence of including all drop-outs, irrespective of their reason, into the group of non-responders, a sensitivity analysis of the primary efficacy endpoint will be conducted for the subgroup of the safety analysis set, excluding all patients who terminated due to a reason not related to glycaemic control. Patients who discontinued due to glycaemic control reasons will continue to be counted as non-responders.

The key secondary objective (safety analysis), the proportion of patients having experienced at least one hypoglycaemic event (confirmed or severe) over the 52-week double-blinded treatment period, will be analysed using the same approach as in the analysis of the primary endpoint. Superiority of saxagliptin will be tested in the safety analysis set.

To preserve the type I error rate ≤ 0.05 (two-sided) across the primary and the key secondary endpoints, a hierarchical testing procedure will be used to interpret the statistical significance of these treatment comparisons. The primary endpoint will be tested first followed by the key secondary endpoint. Both comparisons will be tested at a two-sided significance level of $\alpha=0.05$. However, a comparison of the key secondary objective will only be confirmed as statistically significant if the preceding primary comparison is statistically significant.

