Placebo 1 mg 1-2 mg ² 1-3 mg ² 1-4 mg ²						1-6 mg ², 3	Placebo 1 -6 mg							
	E Saxagliptin 5 mg							Saxagliptin 5 mg						
Week	-6	-4	t .	-2	0	3		6	9	12	24	32	40	52
Visit	s	1		2	3	4		5	6	7	8	9	10	11
				Counselling on dietary and lifestyle modifications according to usual clinic al routine									\rightarrow	

1. Lead-in, placebo 1 mg and placebo 5 mg, single blinded treatment for glimepiride and saxagliptin

2. Indicates dose range for the glimepiride/placebo treatment. Should be based on treatment target FPG ≤6.1 mmol/L or ≤110 mg /dL and the patient's self monitored plasma glucose values.

3. The patients reaching the 6 mg dose at Visit 7 will have a follow-up phone call 3 weeks later

Revised Clinical Study Protocol Drug Substance Saxagliptin Study Code D1680L00002 Edition Number 4.0 Date

The study will consist of 4 periods:

Enrolment Period (Week -4 to -2)

Patients aged 65 years or older with type 2 diabetes with inadequate glycaemic control (HbA_{1c} \geq 7.0 % and \leq 9.0% based on value from screening visit) and currently on a stable monotherapy of metformin (any doses) for at least 8 weeks will be eligible to enter the study. The patient should maintain the prescribed stable dose of metformin for the duration of the study. Blood sampling and other examinations for assessment of inclusion and exclusion criteria will be performed.

Lead-in Period (Week -2 to 0)

Patients who still meet all inclusion and no exclusion criteria are eligible to enter the 2-week single-blind (blind to patient only) placebo lead-in period. The patients will from this period on, and during the entire study, be counselled on dietary and lifestyle modifications according to usual clinical routine. They will be given a glucometer to check their plasma glucose at home on a regular basis and to register the results in the patient diary during the duration of the study. The glucometer measures capillary glucose, and the measured value is recalculated by the glucometer to show plasma values. Hypoglycaemic events should during the entire study period always be entered into the patient hypoglycaemic event diary. For details on hypoglycaemic events and diaries, see Sections 6.4.9 and 6.5, 6.5.1.

Titration Period (Week 0 to 12)

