6.3 Efficacy

The baseline is defined as the assessment at randomisation visit (Visit 3).

Self-monitoring of plasma glucose should be done in order to reduce risk of prolonged periods of undetected hyperglycaemia or to confirm hypoglycaemia. Patients will be asked to do self-monitoring of plasma glucose using glucometers provided by AstraZeneca. The patients will receive instruction on the use of the glucometer, according to the manufacturer's instruction.

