12.2.2 General analyses and exploratory endpoints

The time course of all continuous variables will be presented using standard descriptive summary statistics. Exploratory analyses of continuous endpoints will be performed using ANCOVA methods for the change from baseline. The ANCOVA model will use the factors treatment group and age (<75 versus \geq 75 years) as a fixed effect and the respective baseline value as covariate. Within the framework of the ANCOVA model, point estimates and the two-sided 95% confidence intervals for the mean change within each treatment group, as well as for the differences in mean change between the two treatment groups, will be reported. Repeated measurement analysis by analogy with the ANCOVA model will be conducted, if appropriate.

Categorical variables will be summarized by counts, proportions, and if appropriate, corresponding 95% confidence intervals. Exploratory analyses of categorical endpoints will use the same approach as for the primary endpoint.

Due to the large number of centres and the expected low number of patients per centre, centre effects will not be included in the analysis. Tables by country will be provided in order to explore country effects. Country effects will be included in the statistical models in additional exploratory analyses, if appropriate. Any pooling of countries with few patients in geographical clusters will be specified in the SAP before breaking the blind.

Revised Clinical Study Protocol Drug Substance Saxagliptin Study Code **D1680L00002** Edition Number 4.0 Date

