12.3 Determination of sample size

Based on the available literature and previous trial results, we assume rates of patients reaching HbA_{1c} target without confirmed or severe hypoglycaemia of 57% for the saxagliptin group and of 45.5% for the glimepiride group, corresponding to a 1.59 times higher OR for saxagliptin compared to glimepiride (OR=1.59). As this trial carries a more conservative approach – the group of non-responders including all subjects dropping out due to reasons not related to glycaemic control – sample size calculations use accordingly lowered response rates and OR.

Assuming 10% of patients dropping out due to reasons not related to glycaemic control yields a reduced response rate of 51.3% for the saxagliptin group and of approximately 40.5% for the glimepiride group, based on a more conservative OR of 1.55. Sample size calculation based on the Cochran-Mantel-Haenszel method, using continuity correction and assuming equality of ORs across strata, yields a total of 698 patients, randomised and treated (349 patients in each treatment arm), needed to detect superiority with a two-sided significance level of α =0.05 and 80% power.

The selected sample size should result in a total number of 140 randomised and treated patients aged \geq 75 years per treatment arm (40% of 349).

The sample size for this study was selected to be consistent with the research hypothesis as described in Section 1.2.

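### The primary age-stratified CMH test is valid and has its stated 80% power, but it leaves out baseline HbA1c, which could add up to about 7 points of power at little cost

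*Protocol*

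**What the plan says.** Protocol section 12.2.1, repeated in the synopsis, fixes the primary analysis: the proportion of responders "will be analysed using the Cochran-Mantel-Haenszel (CMH) method for the odds ratio (OR), including a stratification variable for the age group". The two age groups are split at 75 years, and age group is also the only randomisation stratum (section 3.1). The analysis is done on the safety analysis set, and section 12 counts every non-completer as a non-responder.

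Baseline HbA1c is available. Table 2 in section 6.3.1 lists HbA1c at screening and at Visit 3, and sections 6.3 and 11.1.1 make Visit 3 the efficacy baseline. Eligibility is "based on value from screening visit" (section 3.1), so randomised patients should also have a screening HbA1c. Section 12.2.2 analyses change in continuous endpoints by ANCOVA with treatment, age group and "the respective baseline value as covariate". Categorical endpoints follow the primary approach and therefore have no such covariate.

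The sample size in section 12.3 was calculated for the CMH itself. It assumes "a reduced response rate of 51.3% for the saxagliptin group and of approximately 40.5% for the glimepiride group". The odds ratio behind these two rates is 1.55, and the calculation gives 349 patients per arm "needed to detect superiority with a two-sided significance level of α =0.05 and 80% power".

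**The concern.** Entry HbA1c spans 7.0% to 9.0% and the response threshold is below 7%. A patient who starts just above the threshold probably has a better chance of response than one who starts near 9%. The protocol adds a second link: a confirmed HbA1c ≥8.0% between Weeks 12 and 40 is a discontinuation criterion (section 5.8), and non-completion counts as failure. Neither the randomisation nor the primary test takes baseline HbA1c into account.

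In a randomised trial, leaving out a prognostic covariate does not bias the test, but it gives up precision. It also leaves a chance imbalance in baseline HbA1c in the estimated odds ratio. The key secondary hypoglycaemia test can be declared significant only if the primary test is, so power lost on the primary is lost there too.

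**Working it through.** **1. Reproduce the planned sample size.** Inputs from section 12.3: p1 = 0.513, OR = 1.55, two-sided α = 0.05, power 80%, 1:1, continuity correction.

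- Glimepiride odds = (0.513/0.487)/1.55, so p2 = 0.4046. The difference is d = 0.1084 and the mean rate is p̄ = 0.4588.
- Without correction: n0 = [1.96·√(2p̄(1−p̄)) + 0.8416·√(p1(1−p1)+p2(1−p2))]²/d² = 330.7, that is 331 per arm (662 in total).
- With correction: n = (n0/4)·[1 + √(1 + 4/(n0·d))]² = 348.9, that is 349 per arm, **698 in total**. This matches exactly.
- Power at 349 per arm is 80.0% with the correction and 82.1% without it.

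On its own inputs, then, the planned test reaches its target.

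**2. Power with baseline HbA1c added.** The documents give no strength of association, so it is an assumption, shown as an odds ratio per SD of baseline HbA1c from 1.0 (none) to 3.0. Each row is 4,000 simulated trials with 349 per arm, 40% aged ≥75, a normally distributed baseline, and marginal response rates held at 51.3% and 40.46%. The Monte Carlo standard error is about 0.6 points.

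| OR per SD (assumed) | Age-only CMH, uncorrected | Age-only CMH, corrected | Logistic: treatment, age, HbA1c | CMH: age × HbA1c median split |
|---|---|---|---|---|
| 1.0 | 82.5% | 80.8% | 82.3% | 82.1% |
| 1.5 | 82.9% | 81.0% | 84.2% | 83.5% |
| 2.0 | 81.0% | 78.9% | 85.4% | 83.8% |
| 2.5 | 82.1% | 79.8% | 87.4% | 85.7% |
| 3.0 | 82.3% | 80.3% | 89.4% | 87.4% |

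The age-only columns vary only through simulation error, because the marginal rates are fixed. The like-for-like comparison is with the uncorrected CMH. On that basis the logistic gain by row is −0.2, 1.3, 4.4, 5.4 and 7.1 points, and the split-CMH gain is −0.4, 0.6, 2.9, 3.7 and 5.1. A second set of simulated trials gave 0 to 1, about 3, and 6 to 7 points for logistic adjustment at odds ratios of 1.5, 2.0 and 3.0. It gave about 2 and 4 points for the split CMH at 2.0 and 3.0. A fair summary is 0 to 7 points.

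**3. The odds ratio changes meaning.** With the marginal odds ratio held at 1.55, the odds ratio conditional on baseline HbA1c was 1.58, 1.63, 1.68 and 1.73 for assumed odds ratios per SD of 1.5, 2.0, 2.5 and 3.0.

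**4. Chance imbalance.** A 1.96-standard-error difference in mean baseline HbA1c is 1.96·√(2/349) = 0.148 SD. The shift in the unadjusted log odds ratio is about ln(OR per SD) × 0.148 × ln(1.55)/ln(conditional OR).

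- OR per SD 1.5: 0.405 × 0.148 × 0.438/0.456 = 0.058, so 1.55 becomes about 1.46.
- OR per SD 2.0: 0.693 × 0.148 × 0.438/0.486 = 0.093, so 1.55 becomes about 1.41.
- OR per SD 3.0: 1.099 × 0.148 × 0.438/0.545 = 0.131, so 1.55 becomes about 1.36.

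An imbalance this large in either direction occurs in about 5% of randomisations.

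**The case against.** The strongest reply is that nothing is broken. CMH stratified by the sole randomisation factor is a valid test, it needs no model for HbA1c, and the trial was sized for it. That stands, and this point is therefore about efficiency. The contrast with section 12.2.2 is also not an inconsistency: the plan adjusts change scores for baseline and treats all categorical endpoints alike.

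Several stronger readings are tempting, and the documents do not support them.

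- *The trial is underpowered without adjustment.* A reader might infer this from 0.9 × 45.5% = 40.95%, against the stated 40.5%. At 40.95% the odds ratio is 1.52, and power at 349 per arm is 76.1% (corrected) or 78.4% (uncorrected). That is a question about the planning rates in section 12.3, separate from the choice of test. On the stated odds ratio of 1.55 there is no shortfall.
- *Baseline HbA1c is the strongest measured predictor.* The documents rank no predictors. The endpoint also fails patients for hypoglycaemia and for any non-completion. Patients with a low baseline could be more prone to hypoglycaemia under titration to a fasting glucose target, which would partly offset the HbA1c link. The simulation uses a single slope for the whole composite and does not model this.
- *Patients already below 7% at Visit 3 bias the comparison.* Eligibility uses the screening value, so such patients can occur. Randomisation spreads them over both arms in expectation, and the 5% test already allows for chance imbalance. Their share is not given in the documents.

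The reply is also right that adjustment has costs. The safety analysis set requires only one dose, so a missing Visit 3 HbA1c would drop a patient unless a rule is given, and a logistic odds ratio is not the planned one.

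**Conclusion.** The point holds as an efficiency improvement and not as an error. The age-only CMH is valid and meets its 80% target on the protocol's inputs. It leaves out a covariate that is already collected and likely to be prognostic. If the assumed odds ratio per SD is 1.5 to 3.0, adding baseline HbA1c gains roughly 0 to 7 points of power and reduces the effect of chance imbalance on the estimate. If there is no association, it gains nothing. The size rests wholly on that assumed association, on a normally distributed baseline and on a single logistic slope for the composite. The split-CMH figures use a median split. A cut at 8.0% would do about as well only if it divides patients into groups of similar size.

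**What to change.** Amend section 12.2.1 and the synopsis before unblinding so that the primary analysis includes baseline HbA1c, in one of two ways:

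- add a baseline HbA1c category (<8.0%, ≥8.0%) to the CMH strata alongside age group; or
- use logistic regression with treatment, age group and continuous Visit 3 HbA1c.

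With either choice:

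- use the screening HbA1c where the Visit 3 value is missing, so that no patient leaves the safety analysis set;
- keep the non-responder rule unchanged;
- state whether the tested and reported odds ratio is conditional or marginal, and note that a conditional one will be somewhat larger than the planned 1.55;
- keep the age-only CMH as a supportive analysis;
- say whether the key secondary and exploratory categorical endpoints, which are tied to the primary approach, also take the new term.

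The cost is wording in the protocol and the analysis plan, with no new data and no extra patients. The small downside is a choice of model or cut-point and a change in what the odds ratio is conditioned on.

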12.2.2 General analyses and exploratory endpoints

The time course of all continuous variables will be presented using standard descriptive summary statistics. Exploratory analyses of continuous endpoints will be performed using ANCOVA methods for the change from baseline. The ANCOVA model will use the factors treatment group and age (<75 versus \geq 75 years) as a fixed effect and the respective baseline value as covariate. Within the framework of the ANCOVA model, point estimates and the two-sided 95% confidence intervals for the mean change within each treatment group, as well as for the differences in mean change between the two treatment groups, will be reported. Repeated measurement analysis by analogy with the ANCOVA model will be conducted, if appropriate.

Categorical variables will be summarized by counts, proportions, and if appropriate, corresponding 95% confidence intervals. Exploratory analyses of categorical endpoints will use the same approach as for the primary endpoint.

Due to the large number of centres and the expected low number of patients per centre, centre effects will not be included in the analysis. Tables by country will be provided in order to explore country effects. Country effects will be included in the statistical models in additional exploratory analyses, if appropriate. Any pooling of countries with few patients in geographical clusters will be specified in the SAP before breaking the blind.

Revised Clinical Study Protocol Drug Substance Saxagliptin Study Code **D1680L00002** Edition Number 4.0 Date

12.3 Determination of sample size

Based on the available literature and previous trial results, we assume rates of patients reaching HbA_{1c} target without confirmed or severe hypoglycaemia of 57% for the saxagliptin group and of 45.5% for the glimepiride group, corresponding to a 1.59 times higher OR for saxagliptin compared to glimepiride (OR=1.59). As this trial carries a more conservative approach – the group of non-responders including all subjects dropping out due to reasons not related to glycaemic control – sample size calculations use accordingly lowered response rates and OR.

Assuming 10% of patients dropping out due to reasons not related to glycaemic control yields a reduced response rate of 51.3% for the saxagliptin group and of approximately 40.5% for the glimepiride group, based on a more conservative OR of 1.55. Sample size calculation based on the Cochran-Mantel-Haenszel method, using continuity correction and assuming equality of ORs across strata, yields a total of 698 patients, randomised and treated (349 patients in each treatment arm), needed to detect superiority with a two-sided significance level of α =0.05 and 80% power.

The selected sample size should result in a total number of 140 randomised and treated patients aged \geq 75 years per treatment arm (40% of 349).

The sample size for this study was selected to be consistent with the research hypothesis as described in Section 1.2.

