The key secondary objective, the proportion of patients with hypoglycaemic events during the double-blind treatment period, will be analysed using the same approach as in the analysis of the primary endpoint. Superiority of saxagliptin will be tested in the safety analysis set.

To preserve the type I error rate ≤ 0.05 (two-sided) across the primary and the key secondary endpoint, a hierarchical testing procedure will be used to interpret the statistical significance of these treatment comparisons. The primary endpoint will be tested first followed by the key secondary endpoint. Both comparisons will be tested at a two-sided significance level of $\alpha=0.05$. However, a comparison of the key secondary objective will only be confirmed as statistically significant if the preceding primary comparison is statistically significant.

Exploratory analyses of continuous endpoints will be performed using ANCOVA methods for the change from baseline. The ANCOVA model will use the factors treatment group and age (<75 versus \geq 75 years) as a fixed effect and the respective baseline value as covariate.

Exploratory analyses of categorical endpoints will use the same approach as for the primary endpoint.

A total of 698 evaluable patients (349 in each treatment arm) is needed to detect superiority of saxagliptin in the primary analysis with a two-sided significance level of α =0.05 and 80% power under the assumption of a 1.55 times higher odds for reaching HbA_{1c} <7% without hypoglycaemia (confirmed or severe, as defined in Section 6.4.9) with saxagliptin treatment, compared to glimepiride. The selected sample size should result in a total number of 140 evaluable patients aged ≥75 years per treatment arm (40% of 349).

TABLE OF CONTENTS

PAGE

	TITLE PAGE	1
	PROTOCOL SYNOPSIS	2
	TABLE OF CONTENTS	6
	LIST OF ABBREVIATIONS AND DEFINITION OF TERMS	11
1.	INTRODUCTION	13
1.1	Background	13
1.2	Research hypothesis	14
1.3	Rationale for conducting this study	14
1.4	Benefit/risk and ethical assessment	15
2.	STUDY OBJECTIVES	16
2.1	Primary objective	16
2.2	Secondary objectives	16
2.3	Safety objective	16
2.4	Exploratory objectives	16
3.	STUDY PLAN AND PROCEDURES	17
3.1	Overall study design and flow chart	17
3.2	Rationale for study design, doses and control groups	23
3.2.1	Study design and regulatory requirements	23
3.2.2	Study doses and control groups	23
324	Choice of outcome variables	24
3.2.5	Choice of study population	24
4.	PATIENT SELECTION CRITERIA	25

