12. STATISTICAL METHODS AND SAMPLE SIZE DETERMINATION BY ASTRAZENECA

The primary objective of the study will be to show the superiority of saxagliptin compared to glimepiride in elderly patients (\geq 65 years) with type 2 diabetes in regard to the proportion of patients achieving the HbA_{1c} target of <7% without hypoglycaemia (confirmed or severe) after 52 weeks of treatment. Any patient who does not complete the 52-week treatment period will be considered as a non-responder, ie, as having not achieved the HbA_{1c} target without confirmed or severe hypoglycaemia. For definition of hypoglycaemic events, see Section 11.2.3.

The key secondary objective (safety analysis) will be to show the superiority of saxagliptin compared to glimepiride in regard to the proportion of patients having experienced at least one hypoglycaemic event (confirmed or severe) over the 52-week treatment period. A hierarchical testing procedure will be applied in order to control the type I error rate.

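### Section 12.3: 10% drop-out in both arms gives 51.3% versus 40.95% and an odds ratio of 1.52, not the 1.55 behind the 698 patients and 80% power

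*Protocol*

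**What the plan says.** Section 12.3 takes its starting rates from literature and previous trials: "57% for the saxagliptin group and of 45.5% for the glimepiride group", with an odds ratio of 1.59. Because the primary analysis counts drop-outs as failures, "sample size calculations use accordingly lowered response rates and OR". The step itself reads: "Assuming 10% of patients dropping out due to reasons not related to glycaemic control yields a reduced response rate", namely "51.3% for the saxagliptin group and of approximately 40.5% for the glimepiride group, based on a more conservative OR of 1.55". The Cochran-Mantel-Haenszel (CMH) calculation, with continuity correction and a common odds ratio across strata, then gives 698 patients (349 per arm), "needed to detect superiority with a two-sided significance level of α =0.05 and 80% power".

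The introduction to section 12 applies the non-responder rule without regard to arm: "Any patient who does not complete the 52-week treatment period will be considered as a non-responder". The synopsis repeats 698 patients and "80% power under the assumption of a 1.55 times higher odds", but does not mention the drop-out step.

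**The concern.** Section 12.3 gives one drop-out rate for all patients and presents both lowered response rates as its result. The saxagliptin rate is what 10% drop-out produces. The glimepiride rate is lower than 10% drop-out produces, so the gap between the arms, and with it the odds ratio, is larger than the stated assumption supports.

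The sample size is built on that odds ratio. At stake is whether 698 patients carry the stated 80% power for the primary endpoint under the plan's own assumptions. Type I error and the treatment estimate are not affected.

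**Working it through.** **Inputs.** From section 12.3: 57% and 45.5% before drop-out; 10% drop-out counted as non-response; planning values 51.3%, about 40.5% and odds ratio 1.55; two-sided alpha 0.05; 80% power; continuity correction; 349 per arm. The 1:1 allocation is in section 3.1. Age strata of 60% and 40% (sections 3.1 and 12.3) give about 209 and 140 per arm.

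**1. The drop-out step.** Response after drop-out = response before × (1 − 0.10).
- Starting odds ratio: (0.57/0.43) / (0.455/0.545) = 1.588, stated as 1.59.
- Saxagliptin: 0.57 × 0.90 = 51.3%, as stated.
- Glimepiride: 0.455 × 0.90 = 40.95%, not 40.5%.
- Odds ratio: (0.513/0.487) / (0.4095/0.5905) = 1.519, not 1.55.

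**2. What 1.55 implies.** The glimepiride odds are (0.513/0.487)/1.55 = 0.6796, so the rate is 0.6796/1.6796 = 40.46%. The implied drop-out is 1 − 40.46/45.5 = 11.1%. Taking the printed 40.5% instead gives 1 − 40.5/45.5 = 11.0%.

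**3. Reproducing 698.** I used the two-proportion formula. With equal rates and a common odds ratio across strata it approximates the CMH calculation. With d = p1 − p2 and p̄ the mean of the two rates:
- n = [1.960 √(2p̄(1−p̄)) + 0.8416 √(p1(1−p1) + p2(1−p2))]² / d²
- with continuity correction, n_cc = (n/4) [1 + √(1 + 4/(n d))]²

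For 51.3% versus 40.46%: n = (1.3812 + 0.5896)² / 0.10838² = 330.7, and n_cc = 348.9, rounded up to 349 per arm or 698 in total. This is an exact match. The printed 40.5% gives 352 per arm (704), so the calculation was evidently run from the odds ratio.

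**4. The same method at 10% in both arms.** For 51.3% versus 40.95%: n = (1.3817 + 0.5901)² / 0.1035² = 363.0, and n_cc = 382.05, rounded up to 383 per arm. That is 766 in total, 68 more than 698 (+9.7%). Without the correction the total is 726.

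**5. Power at 349 per arm.** Under the null, the standard error is √(2p̄(1−p̄)/349) = 0.03774. Under the alternative it is √[(p1(1−p1) + p2(1−p2))/349] = 0.03753.
- Corrected: z = (0.1035 − 1/349 − 1.960 × 0.03774) / 0.03753 = 0.711, power 76.1%.
- Uncorrected: z = (0.1035 − 1.960 × 0.03774) / 0.03753 = 0.787, power 78.4%.

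Two further checks were made: exact enumeration of the unstratified test, and simulation of the age-stratified CMH test (209 + 140 per arm, same rates in both strata, 400,000 replicates).

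| Power at 349 per arm | Formula | Enumeration | Simulated CMH |
|---|---|---|---|
| 51.3% vs 40.46% (OR 1.55), corrected | 80.0% | 80.7% | 80.6% |
| 51.3% vs 40.95% (OR 1.52), corrected | 76.1% | 76.9% | 76.8% |
| 51.3% vs 40.95% (OR 1.52), uncorrected | 78.4% | 79.1% | 79.0% |

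**The case against.** Several points on the other side are sound, and they limit what can be concluded.

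- **The 698 is not miscalculated.** A reader might infer that the sample-size computation is wrong or that the synopsis makes a false statement. Neither holds. The synopsis gives 80% power conditional on an odds ratio of 1.55, and that conditional statement is correct. The fault lies in how 12.3 gets from 10% drop-out to 1.55.
- **The odds ratio is disclosed.** Section 12.3 says openly that the glimepiride rate is approximate and rests on 1.55. A reader might infer a hidden assumption of unequal drop-out. The text shows only that the link between 10% and 1.55 is unexplained.
- **Calling 1.55 more conservative is not an error.** The comparison is with the 1.59 just before it, and 1.55 is lower.
- **The continuity correction is fixed only for the sample-size calculation.** Section 12.2.1 names the CMH method for the analysis and mentions no correction. If the test is uncorrected, power under the 10% assumption is within 2 points of 80%, so 76% is not the only possible figure.
- **The disputed input is small.** It is about half a percentage point in one arm, and the starting rates are themselves assumptions.

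The discrepancy remains after all of this. The word approximately does not cover it, because 40.95% rounds to 41.0% and 698 reproduces from 1.55, not from 1.52. Nor can the correction be used to set 698 and then ignored: by the plan's own method the stated assumption gives 76.1%, and even without correction 80% would take 726 patients.

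**Conclusion.** Wrong as written; severity minor to moderate. One 10% drop-out rate, applied to both arms as section 12.3 describes, leads to an odds ratio of 1.52. The planning value of 1.55 needs about 11.1% drop-out on glimepiride, for which the protocol gives no statement or reason.

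Under the stated assumption, power at 698 is about 76% by the plan's continuity-corrected formula (about 77% by enumeration or simulation), and 78 to 79% if the CMH test is uncorrected. The shortfall against 80% is therefore roughly 1 to 4 points. These figures assume the starting rates of 57% and 45.5%, the same response rates in both age strata, and that every non-glycaemic drop-out counts as a non-responder.

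A reader might infer that the trial is seriously underpowered or that it must recruit more patients. The size of the shortfall does not support that. What is needed is that the stated assumptions, odds ratio and power agree.

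**What to change.** Reconcile section 12.3 in one of two ways.

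1. Keep 10% drop-out in both arms. Restate the glimepiride rate as about 41.0% (40.95%), the odds ratio as 1.52, and the power at 698 patients as about 76% with continuity correction, 78 to 79% without. Align the odds ratio and power in the synopsis.
2. Keep the odds ratio of 1.55 and 80% power, and state and justify a drop-out of about 11% on glimepiride against 10% on saxagliptin. The synopsis then stands.

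Under either route the description of the odds ratio as more conservative may stay, since it refers to 1.59. The cost is a few words in 12.3 and, under the first route, in the synopsis, plus a less favourable stated power. The sample size of 698 can stay; under the first route the sponsor would be accepting the lower power explicitly.
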